#### Start Date

- If start date is completely missing, or if month and day are missing and year is the same year as baseline (randomization for No Treatment group, first treatment administration for Treatment group), it will be assumed that the AE started at baseline.
- If the start date is missing the day, the baseline day will be used provided the imputed date is on or after the subject's randomization date; otherwise, the day of randomization will be used.
- If the start date is missing the month, the randomization month will be used.
- If the start date is missing the year, the baseline year will be used provided the imputed date is on or after the subject's randomization date; otherwise, the subsequent year after randomization will be used.

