#### 2.5 Safety Analysis

Safety endpoints will be summarized using descriptive statistics by treatment group based on the Safety population using observed cases. There are no planned inferential statistical analyses of safety endpoints.

Subjects in the No Treatment group who elect for an optional treatment will also be included in the Treatment Administration and Adverse Events summaries.

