#### 2.5.2 Adverse Events (AEs)

AEs will be summarized relative to the treatment session timing using the following categories:

- No Treatment at Baseline: Subjects who receive no treatment at baseline, include AEs before any optional *Restylane Lyft Lidocaine* treatment at Month 12.
- Initial Treatment with *Restylane Lyft Lidocaine*: Subjects who were initially treated with *Restylane Lyft Lidocaine* at Baseline.
- Optional Treatment at 12 Month Visit: Subjects who received no treatment at baseline and were treated with *Restylane Lyft Lidocaine* at the 12 month visit. Includes AEs that occur after optional treatment.

• Total *Restylane Lyft Lidocaine*: Includes all subjects who were initially treated with *Restylane Lyft Lidocaine* at baseline or treated at the optional 12 month visit.

All AEs will be coded according to MedDRA and summarized by System Organ Class (SOC), Preferred Term (PT), and treatment. The number of subjects with at least one event, associated percentage, and number of events will be provided.

For subject counts, a subject will only be counted once per SOC and once per PT in cases where multiple events are reported for a subject within SOC or PT. For event counts, subjects with multiple events in a category will be counted for each event.

The number of subjects with AEs related to study product or study product injection procedure and unrelated AEs will be presented by SOC, PT, and maximum intensity. Action taken for related AEs will also be summarized by SOC and PT using number of events.

Serious AEs (SAEs) will be listed.

For AEs related to study product or study product injection procedure, the number of days to onset and the duration of event will be summarized by SOC and PT using mean, standard deviation, median, minimum, and maximum. Days to onset of an AE will be derived as the start date minus the date of most recent treatment session. Duration of an AE will be derived as the stop date minus the start date + 1.

For the purpose of deriving days to onset and duration, the following date imputation rules will be used.

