# End Date

- If end date is completely missing, it will be assumed that the AE is still ongoing and will not be imputed.
- If the end date is missing the day, the last of the month will be used (i.e. UNK-JAN-2022 becomes 31-JAN-2022)
- If the end date is missing the month, the subsequent month after the start date will be used.
- If the end date is missing the year, the year of randomization will be used, provided the imputed date is after the start date; otherwise, the subsequent year after start date will be used.

Adverse events with a completely missing start date will be considered treatment-emergent unless the event has a stop date prior to the date of the first dose of study drug. All AEs will be listed by treatment and subject. Dates will be presented as collected in the listings.

In addition, a summary of all AEs will be provided, which will include (but is not limited to):

Version: 1.0

GALDERMA	05DF22
EST 1981	

- number of subjects with at least one AE and number of events (in total as well as SAEs),
- number of subjects with at least one related AE and number of events (in total as well as SAEs),
- number of subjects with at least one unrelated AE and number of events (in total as well as SAEs),
- number of subjects who did not have an AE.

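### The SAP's partial-date rules for adverse events can add about a year to a duration, or give negative values and non-existent dates; correct the end-year rule and bound the imputed dates

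*SAP*

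**What the plan says.** SAP 2.5.2 states the purpose of the rules: "For the purpose of deriving days to onset and duration, the following date imputation rules will be used". It defines onset by "Days to onset of an AE will be derived as the start date minus the date of most recent treatment session" and duration as stop minus start plus 1. Both are summarized for related AEs by system organ class and preferred term, with mean, SD, median, minimum and maximum. Onset and duration belong to the first safety endpoint (SAP 1.2.3).

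The rules at issue are:

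- **Start day missing:** "If the start date is missing the day, the baseline day will be used provided the imputed date is on or after" the randomization date; failing that, the day of randomization.
- **Start month missing:** "If the start date is missing the month, the randomization month will be used", with no condition attached.
- **Start wholly missing:** "it will be assumed that the AE started at baseline".
- **End day missing:** the last day of the month.
- **End month missing:** "If the end date is missing the month, the subsequent month after the start date will be used".
- **End year missing:** the randomization year, "provided the imputed date is after the start date; otherwise, the subsequent year after start date will be used".

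SAP 2.5 adds: "Subjects in the No Treatment group who elect for an optional treatment will also be included in the Treatment Administration and Adverse Events summaries". Their optional treatment comes 12 months after baseline, which the study counts as 48 weeks.

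**The concern.** No rule checks that an imputed date exists, that an imputed start is no later than a recorded stop, or that it is no earlier than the treatment session the AE followed. The day and year rules for the start carry a check against randomization; the month rule does not. The end-year rule has a separate logical fault: when an AE starts in a later calendar year than randomization, the start year itself is never tried. The study lasts about 18 months (Protocol 3.4), so it must cross a calendar year.

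At stake are descriptive safety figures. In a system organ class or preferred term cell with few events, one wrong value sets the minimum or maximum and pulls the mean. A negative number is likely to be noticed; a positive duration of about a year is easier to miss.

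**Working it through.** **Inputs.** The rules and the onset and duration formulas come from SAP 2.5.2. One month is 4 weeks (SAP 1.3), so Month 12 is 12 × 28 = 336 days. Day 1 is taken as both baseline and randomization. The calendar dates below are illustrative; the documents give none.

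**The SAP's own example.** An end date of January 2022 with the day missing becomes 31-JAN-2022. This reproduces.

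**End year missing.** The rule works when the start is in the randomization year and the end is on a later day. It fails in two situations.

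- *Start in a later year.* Randomized 2022, start 05-Feb-2023, end 09-Feb with no year. 09-Feb-2022 is not after the start, so the rule takes 2023 + 1 = 2024. Duration = 09-Feb-2024 − 05-Feb-2023 + 1 = 369 + 1 = 370 days, not 5.
- *Same-day AE.* The end equals the start and so is not after it. For 05-Feb-2023 the end becomes 05-Feb-2024: 365 + 1 = 366 days. For 10-Mar-2023 it becomes 10-Mar-2024: 366 + 1 = 367 days. The true value is 1.

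The Month 12 session is especially exposed. In a non-leap year, anyone randomized on or after 30 January (day 30 + 336 = day 366) has a nominal Month 12 date in the next calendar year. For example: randomized 21-Nov-2022, treated 23-Oct-2023, AE from 24-Oct-2023 to 28-Oct with no year. The rule gives 28-Oct-2024: 370 + 1 = 371 days, not 5.

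**Start day missing.**

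- Baseline 24-Jan-2023, start in February 2023, stop 06-Feb-2023. The imputed start is 24-Feb. Duration = 6 − 24 + 1 = −17 days.
- A baseline day of 31 with a start in April gives 31-APR, which does not exist.

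**Start month missing.** Baseline 20-Mar-2023, start on the 5th of an unknown month in 2023. The imputed start is 05-Mar-2023. Onset = 5 − 20 = −15 days.

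**Start wholly missing.** The control subject above, treated 23-Oct-2023, has an AE that stopped on 28-Oct-2023. The start is set to 21-Nov-2022, 336 days before the only session. Duration = 341 + 1 = 342 days.

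**End month missing.** Start 10-Dec-2023, end on the 20th of an unknown month in 2023. The month after December is January. If the recorded year is kept, the end is 20-Jan-2023 and duration = −324 + 1 = −323 days.

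**End day missing.** The same control subject's nominal last visit is 23-Oct-2023 + 14 days = 06-Nov-2023. An end in November 2023 becomes 30-Nov-2023, 24 days after that visit.

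**Effect on a summary.** Take 20 events, 19 lasting 5 days and one imputed at 370: (19 × 5 + 370) / 20 = 465 / 20 = 23.25 days, against 5 if all were 5. The maximum becomes 370.

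**The case against.** The strongest objection is that this will hardly ever matter. Protocol 7.4.6 asks for start and stop dates, subjects are questioned about AEs at each visit (Protocol 7.7), and the eCRF has checks for incomplete data and a query process (Protocol 10.4.1). The month and year rules apply only in the odd pattern where a day is recorded but the month or year is not. Outputs are independently reviewed (SAP 2.1.1), safety endpoints have no inferential analysis, and listings show dates as collected. All of this stands and keeps the point small. It does not make the rules right: a program that returned 370 days would be implementing the SAP correctly, and a correction made at output review would be a choice made after seeing the data.

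Some details are also open to a kinder reading. For the initial session, the randomization check does prevent a negative onset under the start-day rule. The −323 days depends on keeping the recorded year. With a wholly missing start at Month 12, the onset depends on whether the most recent session is judged from the imputed or the true date.

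A reader might go further and infer that a large share of AEs will be affected, or that an imputed start is shown to fall after the subject's last visit. The documents support neither. They give no count of partial dates, and any share depends on assumed recruitment windows and onset times. For a subject randomized on 21-Nov-2022 with a start on the 5th of an unknown month in 2023, the month rule gives 05-Nov-2023, which is 349 days after randomization. That is past the nominal 12-month visit at 336 days but inside its ±14-day window.

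**Conclusion.** The rules are wrong as written, most clearly the one for a missing end year. The size is minor. The effect is limited to descriptive onset and duration summaries of related AEs with partial dates, and no frequency is claimed. Individual errors can be large: about a year for the end-year rule, and negative or impossible values for the others. AE intensity, diary results and the effectiveness analyses are unaffected, and a reader should not infer that the main safety or effectiveness conclusions are in doubt. The one possible spill-over is that a wholly missing start in a control subject treated at Month 12 could place the AE in the no-treatment period.

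The conclusion assumes that the rules are programmed literally and that Day 1 is the randomization date.

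**What to change.** Amend SAP 2.5.2 as follows.

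- **(a) End year missing.** Use the earliest year that puts the end on or after the start. The examples of 370 and 371 days become 5, and the same-day cases become 1.
- **(b) Bounds on every imputed date, including a missing end day.** The date must exist. A start must be on or after randomization and not after the recorded stop. An end must be on or after the start and not after last contact, counting AE follow-up after study end (Protocol 7.4.5.1).
- **(c) Treatment session.** For a related AE in a control subject treated at Month 12, do not impute the start before that session. The 342-day example then starts on 23-Oct-2023, with onset 0 and duration 6. Apply the same to the touch-up only where the record shows that the AE followed it, because the AE fields in Protocol 7.4.6 do not include the session.
- **(d) When the SAP value fails a bound.** If only the day is missing, move to the nearest date that meets the bounds and matches the recorded parts. 31-APR becomes 30-APR, and the −17-day example starts on 06-Feb-2023, with duration 1 and onset 13. If the start month is missing, query; if unresolved, leave onset and duration missing. Treat a failing end month the same way for duration.

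The earliest matching month should not be the fallback for a start. Take a subject randomized and treated on 21-Nov-2022, with a start on the 5th of an unknown month in 2023, a true start of 05-Sep and a stop on 10-Sep-2023. The SAP value, 05-Nov-2023, falls after the stop. The earliest match, 05-Jan-2023, would give 248 + 1 = 249 days instead of 6.

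Report the number of imputed dates. The cost is SAP wording and one derivation program; the rules use recorded data, apart from any queries. There are three downsides: the end-year rule understates a rare event truly lasting more than a year, moving a start back to the stop date gives the shortest possible duration, and a few values will be missing.

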# End Date

- If end date is completely missing, it will be assumed that the AE is still ongoing and will not be imputed.
- If the end date is missing the day, the last of the month will be used (i.e. UNK-JAN-2022 becomes 31-JAN-2022)
- If the end date is missing the month, the subsequent month after the start date will be used.
- If the end date is missing the year, the year of randomization will be used, provided the imputed date is after the start date; otherwise, the subsequent year after start date will be used.

Adverse events with a completely missing start date will be considered treatment-emergent unless the event has a stop date prior to the date of the first dose of study drug. All AEs will be listed by treatment and subject. Dates will be presented as collected in the listings.

In addition, a summary of all AEs will be provided, which will include (but is not limited to):

Version: 1.0

GALDERMA	05DF22
EST 1981	

- number of subjects with at least one AE and number of events (in total as well as SAEs),
- number of subjects with at least one related AE and number of events (in total as well as SAEs),
- number of subjects with at least one unrelated AE and number of events (in total as well as SAEs),
- number of subjects who did not have an AE.

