7.4.5 Follow-up of adverse events

7.4.5.1 Follow-up of unresolved events ongoing at termination of the study

All serious as well as non-serious AEs with a causal relationship to the study product or treatment procedure and ongoing at study end / or ongoing when subject early terminated study participation / or ongoing if study is temporarily halted, shall be followed up after the subject's participation in the study is over. Such events shall be followed-up until resolved, assessed as chronic or stable, or subject is lost to follow up. Final outcome after the end of the study shall be reported on the AE Follow-up form. Other AEs will be monitored until the last visit if they have not resolved or reached a stable condition.

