# 1.2.3 Safety Objectives and Endpoints

To evaluate the safety of *Restylane Lyft Lidocaine* by assessments of adverse events (AEs) by the Treating Investigator throughout the study period.

- 1. Incidence, intensity, duration, and onset of AEs collected during the study period post treatment.
- 2. Pre-defined, expected, post-treatment events reported for 28 days from treatment as recorded in the subject diary.

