#### 2.4.2 Handling of Missing Data

Number of missing values will be summarized and reported as appropriate.

For the ITT analysis of the Blinded Evaluator GJS Responder rate at Month 3 after last treatment for Treatment group (primary endpoint), missing values will be assumed to be

	Title	Doc id
	05DF2209 Statistical Analysis Plan (SAP)	
GALDERMA		MA-58293
EST, 1981		WIA-30293

missing due to lack of effect. Therefore, the primary method of imputation will use the baseline observation carried forward (BOCF) method. Impact of missing data on the primary endpoint will be evaluated by performing sensitivity analysis based on the observed cases, as well as worst-case (No Treatment group imputed as responder, Treatment group imputed as non-responder) and best-case (Treatment group imputed as responder, No Treatment group imputed as non-responder) imputation in the ITT set.

All other effectiveness endpoints will be evaluated based on the observed cases in ITT.

Descriptive statistics of all safety data will be performed on observed cases in the Safety population.

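### Related AEs that never receive a stop date drop out of the AE duration summary, which may therefore run short for persistent events and for controls treated at Month 12

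*SAP*

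**What the plan says.** AE duration is a stated safety endpoint. SAP 1.2.3 lists "Incidence, intensity, duration, and onset of AEs collected during the study period post treatment".

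SAP 2.5.2 gives the derivation: "Duration of an AE will be derived as the stop date minus the start date + 1". For related AEs, "the duration of event will be summarized by SOC and PT using mean, standard deviation, median, minimum, and maximum". No method for open events is named.

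The End Date rules in the same section treat two cases differently:
- No end date at all: "If end date is completely missing, it will be assumed that the AE is still ongoing and will not be imputed".
- Day missing: "If the end date is missing the day, the last of the month will be used". Partial dates are completed, so those events stay in the summary.

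SAP 2.4.2 adds: "Descriptive statistics of all safety data will be performed on observed cases in the Safety population".

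Protocol 7.4.5.1 covers related AEs still open when a subject leaves the study: "Such events shall be followed-up until resolved, assessed as chronic or stable, or subject is lost to follow up". It continues: "Final outcome after the end of the study shall be reported on the AE Follow-up form". The SAP does not mention that form.

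**The concern.** An event without a stop date has no duration under the SAP formula, so it is left out of the mean, SD, median, minimum and maximum. If follow-up time is unrelated to how long an event lasts, longer events are more likely to be open when follow-up ends. The closed events then tend to be the shorter ones.

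The protocol expects some open events, since ongoing is one of the outcome categories in Protocol 7.4.6. SAP 2.5.2 plans no count of ongoing related AEs beside the duration table. A reader of the study report could see a short mean duration with nothing next to it to show that persistent events were excluded.

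Controls who take the optional treatment at Month 12 are the most exposed group. Their last scheduled visit is about 2 weeks later. SAP 2.5.2 also pools them with the Treatment group, followed for 48 weeks, in its category for all subjects given the product.

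**Working it through.** The documents give no AE durations and no share of unresolved events, so there is no figure of the plan's own to reproduce. The check has two parts: which events are lost, and how large the effect could be under stated assumptions.

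**1. Which related events lose their duration**

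| Event | Stop date available? | In the duration summary? |
|---|---|---|
| Resolved during the study | Yes | Yes |
| End date partly missing | Completed by rule | Yes |
| Open at exit, resolves later | Only through the AE Follow-up form | Not stated |
| Judged chronic or stable | No | No |
| Open when subject is lost to follow-up | No | No |

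**2. Possible size, exponential model (assumed)**

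Let durations be exponential with true mean m, observed from onset for τ days, with nothing recorded after τ. Then:
- share still open: c = exp(−τ/m)
- mean of closed events: m − τc/(1 − c)

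Inputs: τ = 336 days (48 weeks, the planned follow-up of the Treatment group) and τ = 14 days (the optional-treatment visit). The values of m are assumptions. The one-day increment in the SAP formula is ignored.

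Example, m = 14 and τ = 14: c = exp(−1) = 0.368, and the mean of closed events is 14 − 14 × 0.368/0.632 = 5.9 days.

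| True mean m (days) | τ = 14: open | τ = 14: closed-event mean | τ = 336: open | τ = 336: closed-event mean |
|---|---|---|---|---|
| 7 | 14% | 4.8 | 0% | 7.0 |
| 14 | 37% | 5.9 | 0% | 14.0 |
| 28 | 61% | 6.4 | 0% | 28.0 |
| 90 | 86% | 6.8 | 2.4% | 81.8 |

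The median behaves in the same way: for m = 14 and τ = 14, the closed-event median is 5.3 days against a true 9.7. The optional-treatment visit has a window of ±7 days. For m = 14, the closed-event mean is 3.2 days at τ = 7 and 8.0 days at τ = 21.

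**3. Effect on the pooled category**

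Take m = 14 and one related event per subject. Assume 105 subjects followed for 48 weeks, all 35 controls treated and leaving at 14 days, and no post-exit dates used. Closed events: 105 + 35 × 0.632 = 127.1. Mean: (105 × 14.0 + 22.1 × 5.9)/127.1 = 12.6 days against 14. Even on these assumptions the pooled mean is about 10% short (12.6/14 = 0.90), whereas the optional-treatment category alone is at 42% of the true mean (5.9/14).

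**4. Persistent events**

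If closed events average 10 days (assumed) and a share f is still open after at least 168 days (assumed), the table shows 10 days. The true mean is at least (1 − f) × 10 + f × 168.
- f = 0: 10 days, no bias.
- f = 5%: 9.5 + 8.4 = 17.9 days.
- f = 10%: 9.0 + 16.8 = 25.8 days.

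Nothing in the documents says that f is above zero.

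**The case against.** **Post-study follow-up.** The summary covers related AEs, and Protocol 7.4.5.1 requires exactly those events to be followed after exit. A reader might infer that follow-up cannot help because the outcome goes on another form. The documents do not support that: neither says that dates on the AE Follow-up form are left out of the derivation. If they are used, the 14-day figures above overstate the loss, and only chronic, stable and lost-to-follow-up events remain missing. This objection stands in part. The SAP is silent, and those remaining events still have no stop date.

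**The longest events.** A reader might also infer that the excluded events are always the longest. That is a tendency only, because an event starting shortly before the last visit can be open and short.

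**Other rules lengthen durations.** A missing end day becomes month end, and a completely missing start date becomes baseline. Both can push durations up, so the net direction in the final table is not fixed. These rules act on events with incomplete dates, however, and do not bring open events back into the summary.

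**Open events can be seen elsewhere.** All AEs are listed with dates as collected, event counts by SOC and PT include them, and SAP 2.1.2 has quantitative summaries generally show the number of subjects. For the Treatment group, SAP 2.5.3 also summarises diary days with each expected reaction, independently of this rule. That is fair, but a listing does not correct a summary statistic. The diary runs for 28 days, and Protocol 7.2 assigns it to the Treatment group only.

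**Expected reactions are short.** Protocol 1.3 and 5.4.3 expect injection reactions to resolve in days to a few weeks. For such events in the Treatment group, the table above shows essentially no bias.

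**Conclusion.** The point holds as a limited one. Under the SAP's own rules a related AE that never gets a stop date is absent from the duration statistics, which tends to make reported durations too short whenever such events exist. The direction assumes that follow-up time does not depend on event length.

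The size cannot be known from the documents. It is zero if every related event resolves with a date, and negligible for short reactions in the Treatment group. It could be large for persistent events, and for the optional-treatment category if post-exit dates are not used. That category holds at most about 35 subjects (a quarter of 140).

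A reader might conclude that the safety evaluation as a whole is compromised. The documents do not support that. AE incidence and intensity and the time to onset do not use the stop date, and no inferential safety analysis is planned. This is a worthwhile improvement to one descriptive table.

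**What to change.** Amend SAP 2.5.2 before database lock:

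1. Show the number of ongoing related AEs beside each SOC and PT duration summary.
2. State that stop dates from the AE Follow-up form enter the duration derivation.
3. Treat events still open as censored at last contact. Give a Kaplan-Meier median for related AEs overall and where event numbers allow. Where a SOC or PT has only a few events, list the minimum duration to last contact instead. A Kaplan-Meier summary for every PT would be impractical.

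The cost is somewhat more table work than one extra column, plus making sure that the AE Follow-up form dates reach the analysis data. The form is already required, so no new assessment is needed. Reported durations may lengthen.
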